2.1.2 Secondary

- (1) **Objective:** To assess the effect of treatment with odanacatib 50 mg once weekly on the risk of clinical vertebral fractures compared to placebo.

Hypothesis: Treatment with odanacatib reduces the risk of clinical vertebral fractures compared to placebo.

- (2) **Objective:** To assess the effect of treatment with odanacatib 50 mg once weekly on height compared to placebo.

Hypothesis: Treatment with odanacatib reduces height loss compared to placebo.

- (3) **Objective:** To assess the effect of treatment with odanacatib 50 mg once weekly on the lumbar spine, total hip, femoral neck, trochanter and distal forearm BMD compared to placebo.

Hypothesis: Treatment with odanacatib increases lumbar spine, total hip, femoral neck, trochanter, and distal forearm BMD compared to placebo.

Product: MK-0822

8

Protocol/Amendment No.: 018-04

- (4) **Objective:** To assess the safety and tolerability of treatment with odanacatib 50 mg once weekly compared to placebo.

Hypothesis: Odanacatib is safe and well tolerated compared to placebo.

- (5) **Objective:** To assess the effect of treatment with odanacatib 50 mg once weekly on biochemical indices of bone resorption (serum C-Telopeptides of Type 1 collagen [s-CTx] and urine N-Telopeptides of Type 1 collagen [u-NTx]) compared to placebo.

Hypothesis: Treatment with odanacatib decreases biochemical indices of bone resorption (s-CTx and u-NTx) compared to placebo.

- (6) **Objective:** To assess the effect of treatment with odanacatib 50 mg once weekly on lumbar spine, total hip, femoral neck, and hip trochanter BMD compared to placebo, in patients who are bisphosphonate-intolerant (i.e. patients with a contraindication or history of intolerance to bisphosphonates, or those considered by their physician to be unsuitable for bisphosphonate treatment).

Hypothesis: Treatment with odanacatib increases lumbar spine, total hip, femoral neck, and hip trochanter BMD compared to placebo in patients who are bisphosphonate-intolerant (i.e. patients with a contraindication to or a history of intolerance of oral bisphosphonate use).

- (7) **Objective:** To assess the effect of treatment with odanacatib 50 mg once weekly on biochemical indices of bone formation (serum bone-specific alkaline phosphatase [BSAP] and serum N-Terminal Propeptides of Type 1 collagen [s-P1NP]) compared to placebo.

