Secondary efficacy endpoints include clinical vertebral fractures, height, BMD measures at different sites, and biochemical markers of bone resorption. Statistical testing for the secondary endpoints will only be performed if the treatment difference for the first primary endpoint (vertebral fractures) is significant. For the purpose of addressing the issue of multiplicity adjustment, BMD measures will be considered as one family. Biochemical markers of bone resorption will be considered another family and clinical vertebral fractures and height a third family. Within each family a Hochberg multiplicity adjustment procedure will be used to ensure a global type I error rate of 5% within each of the groups (conditional on significance at later time points for height and BMD and conditional on significance at earlier time points for biomarkers). No adjustment for multiplicity between the families will be applied. Multiple testing over time will be

Product: MK-0822

21

Protocol/Amendment No.: 018-04

handled by a step-down procedure starting from the last time point for BMD and height and from the earliest time point for biomarkers, until the first non-significant time point.

Significance of the analyses of BMD endpoints in the subgroup of (oral) bisphosphonate intolerant patients will only be concluded if there was a significant result for the analysis for the same BMD endpoint at the same timepoint for the full FAS population.

Interim Analyses

A Data Monitoring Committee (DMC) will monitor the safety of the patients in the study on a regular basis and will review efficacy results from the first formal efficacy interim analysis onwards, as detailed in the DAS of the protocol.

Before the first formal efficacy interim analysis, the DMC will mainly review safety and the study should not be terminated early for efficacy. The same efficacy alpha spending function will be used in these interim analyses as for the 2 formal efficacy interims. From the first formal interim analysis onwards, the DMC will review both efficacy and safety and may recommend early termination of the trial for efficacy if strong evidence (significance) is seen for all three primary endpoints. An alpha-spending function approach will be used to handle the multiplicity due to these formal efficacy interim analyses. Details on the actual alpha levels are in the DAS.

Sample Size and Power

Full detail of the sample size and power calculations is in the DAS (Section 3.5).

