3.5.3 Efficacy/Pharmacokinetics/Safety Variables/Time Points of Interest**Primary Endpoints**

The primary focus of this study will be on fracture incidence, specifically morphometric vertebral, non-vertebral and hip fractures. Lateral thoracic and lumbar spine radiographs will be obtained for each patient at baseline, Month 6, Month 12, and yearly thereafter. The first primary endpoint will be the first morphometrically assessed vertebral fracture per patient determined from the 6-month and yearly radiographs, analyzed as interval-censored survival data. All available x-ray data will be included in the analyses and time windows are in appendix 6.7 to define timing.

All reported fractures, other than fractures of the fingers, toes, and face, will be adjudicated centrally via radiology reports and/or x-rays. Clinical fractures will be identified as being either osteoporotic, or caused by trauma, stress, or pathology. Efficacy analyses of clinical fractures will be based on adjudicated osteoporotic fractures.

For clinical hip and non-vertebral fractures, the time to first fracture will be the main metric for analysis. For example, for a patient who has a wrist fracture and later in time a hip fracture, the time to the wrist fracture will be used in the analysis of non-vertebral fractures and the time to the hip fracture will be used in the analysis of hip fractures. The hip fracture of this patient will not be used in the analysis of time to first non-vertebral fractures. Cumulative incidences of fractures for Month 6 and each of the yearly time points will be summarized. Time to first hip and non-vertebral fracture will be the second and third primary endpoints. Analysis of clinical fractures will be based on adjudicated fractures.

Product: MK-0822

43

Protocol/Amendment No.: 018-04

Secondary Endpoints

Formal testing will be performed for secondary endpoints with an associated hypothesis. For secondary endpoints without an associated hypothesis, p-values will be provided for informational purposes. The multiplicity adjustment strategy for the formal hypothesis tests is described in Section 3.5.5.3.

Clinical Vertebral Fractures

Time to first (adjudicated osteoporotic) clinical vertebral fracture will be a secondary endpoint and will be handled similarly as hip and non-vertebral fractures.

Height

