Two height measurements will be taken and recorded on the eCRF. If the 2 measurements differ by 4 mm or more, a third and fourth measurement will be obtained and recorded on the eCRF. The mean of the last 2 measurements will be used as the estimate of stature.

Change from baseline in stature at each of the yearly timepoints will be secondary endpoints. The number (percentage) of patients with a stature loss of greater than 1 cm during the study will also be analyzed, as will the rate of stature loss.

Height measurements performed on non-calibrated stadiometers or otherwise not obtained according to protocol procedures will be excluded from the analyses. Details on the criteria for exclusion from analysis will be documented in a memo before unblinding the team for the final analysis.

Secondary Bone Mineral Density Endpoints

The percent change from baseline in BMD measurements at the lumbar spine, total hip, femoral neck, trochanter, and 1/3 distal forearm will also be secondary endpoints. BMD measurements will be performed at baseline and each of the yearly timepoints.

For the lumbar spine (posterior/anterior [PA] view) measurements, mean BMD values from at least three evaluable vertebrae (four when available) from L1 to L4 will be used. If a vertebra becomes fractured during the study or was fractured at baseline, BMD data for this vertebra will be excluded from all analyses.

For the hip BMD measurement, the side of the hip measured must be consistent throughout the entire study. If the hip side that is being measured becomes fractured during the study, then data of that hip side will be excluded from the time of the fracture onward.

All analyses of BMD efficacy endpoints will incorporate the longitudinal BMD correction factor as determined by a single quality control center.

Product: MK-0822

44

Protocol/Amendment No.: 018-04

BMD at the total body and 1/3 distal forearm will only be performed in a random 10% subset of the randomized patients, identified by the IVRS system

Biochemical Markers of Bone Resorption and Bone Formation

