In addition, the percentage of patients who experienced a stature loss of greater than 1 cm during the study will be tabulated. A logistic model will be used to compare the two treatment groups, including terms for treatment, geographic region and stratum. The model-based odds ratio, and 95% confidence interval, will be provided as an estimate of the treatment effect.

The rate of stature loss will also be examined, using a mixed model with fixed effects for treatment, geographic region, stratum, treatment-year interaction and random intercept and slope (year). The within patient serial correlation of the values over time will be modeled by an unstructured covariance matrix. The magnitude of the slopes (rate of stature loss) will be summarized from the model, as well as the difference between treatments (mean and 95% CI). More detail on this mixed model is in appendix 6.7.

Bone Mineral Density Endpoints

For each body site and timepoint, BMD will be summarized at baseline and follow-up, by the mean and standard error, together with the mean percent change from baseline and its 95% confidence interval.

The percent change from baseline in BMD endpoints at all during-treatment time points will be analyzed using a longitudinal model with fixed effects for treatment, stratum, geographic region, and treatment-by-time interaction¹. The within patient serial correlation of the values over time will be modeled by an unstructured covariance matrix. More detail on this longitudinal model is in appendix 6.7.

The treatment effect at each of the on-treatment time points will be assessed by evaluating the within- and between-treatment group Least-Squares means (LS mean) and the associated 95% confidence intervals. Treatment difference will be tested at each of the on-treatment time points and adjustment for multiple testing will be handled as discussed below.

Similar analyses will be performed in the subgroup of bisphosphonate-intolerant patients (defined as patients with a contraindication or history of intolerance to bisphosphonates, or those considered by their physician to be unsuitable for bisphosphonate treatment).

A graphical presentation of the LS mean (+/-SE) change from baseline over time will also be provided.

Biochemical Markers

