For biomarkers, a similar approach will be taken, starting from the earliest time point to the last time point where significance is claimed. This approach for biomarkers is taken because the treatment difference is not expected to increase over time after the first on-treatment time point (Month 6), while for BMD and height it is expected to increase.

Significance of the analyses of BMD endpoints in the subgroup of (oral) bisphosphonate intolerant patients will only be tested if the test for the same BMD endpoint in the full FAS population is significant after Hochberg adjustment procedure.

Product: MK-0822

60

Protocol/Amendment No.: 018-04

Alpha Adjustment for Interim Analyses

A DMC will monitor the safety of the patients in the study on a regular basis and will review efficacy in the formal efficacy interims. Before the first formal efficacy interim analysis, the DMC will mainly review safety and the study should not be terminated early for efficacy. To limit the effect of the interim analyses in this time frame on the final alpha level, a low alpha level will be used based on the same spending function used for the formal efficacy interim analyses. From the first formal efficacy interim onwards, the DMC will review both efficacy and safety and may recommend early termination of the trial both for efficacy or for safety. An alpha-spending function approach [25] will be used to handle the multiple looks due to these interim analyses. Details on the actual alpha levels are in Section 3.5.5.6.

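### Once the full-population BMD tests are positive, nothing written in the plan controls error across the four BMD sites of the bisphosphonate-intolerant hypothesis

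*Protocol*

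**What the plan says.** Section 2.1.2 lists as a formal secondary hypothesis: "Treatment with odanacatib increases lumbar spine, total hip, femoral neck, and hip trochanter BMD compared to placebo in patients who are bisphosphonate-intolerant". Section 3.5.2 repeats it, and section 3.5.3 gives its status: "Formal testing will be performed for secondary endpoints with an associated hypothesis". For BMD, section 3.5.3 says that "BMD measurements will be performed at baseline and each of the yearly timepoints". Section 3.5.5.1 says of the full FAS that "Treatment difference will be tested at each of the on-treatment time points and adjustment for multiple testing will be handled as discussed below", and then: "Similar analyses will be performed in the subgroup of bisphosphonate-intolerant patients".

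Section 3.5.5.3 handles multiplicity for the secondary endpoints as follows.

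- No secondary endpoint can be declared significant unless morphometric vertebral fractures are significant.
- The BMD family is total hip, femoral neck, trochanter, lumbar spine and distal forearm, tested by Hochberg at 5% within the family.
- BMD and height step down over time, starting from the last time point performed in at least half the patients.
- For the bisphosphonate-intolerant subgroup, significance "will only be tested if the test for the same BMD endpoint in the full FAS population is significant after Hochberg adjustment procedure".

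Section 2.7 words the subgroup rule differently. Significance "will only be concluded if there was a significant result for the analysis for the same BMD endpoint at the same timepoint" in the full FAS. Section 3.5.5.3 does not mention the time point.

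Section 3.5.5.4 powers the subgroup comparison with 1,400 patients per group, SD 4% and alpha of at least 4.5%, a level adjusted for the interims only.

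**The concern.** The gate links each subgroup site to the same site in the full FAS. It does not link the four subgroup sites to each other. Neither section 3.5.5.3 nor section 2.7 names the subgroup tests as members of the BMD Hochberg family, and the subgroup power paragraph makes no allowance for four sites. Followed as written, each site whose gate is open is tested in the subgroup at the full level.

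The gate offers least where a separate subgroup hypothesis matters most, that is, when the drug works overall but might not work in this population. The plan's own standard is a 5% familywise rate within each family, and it meets that standard for these same four sites in the full FAS. A claim for a defined population could then rest on one site out of four at an unadjusted level. Section 3.5 and Appendix 6.7 say that the content of the stand-alone SAP now sits in this protocol, so the rule has not been left to another document.

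**Working it through.** **1. The plan's own figures.** Subgroup inputs (section 3.5.5.4): n = 1,400 per group, difference 1%, SD 4%, two-sided alpha 0.045.

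- SE = 4 × √(2/1400) = 0.151, so z = 1/0.151 = 6.61.
- Power = Φ(6.61 − 2.00), above 99.9%. The stated figure of more than 99% reproduces, and does so with SD 3% too.
- Full FAS with 6,000 per group: the difference detectable with 99% power is 4 × √(2/6000) × (1.96 + 2.33) = 0.31%, matching the stated 0.3%.

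**2. Is the gate open when the subgroup is null?** Take 16,300 patients, or 8,150 per group, of whom 1,400 are in the subgroup. If the other 6,750 gain 1% and the subgroup gains nothing, the FAS effect is 6,750/8,150 × 1% = 0.83%. Its SE is 4 × √(2/8150) = 0.063, so z is about 13. Even at the strictest Hochberg level for five sites (0.05/5), the gate opens with probability about 1.

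**3. Error in the subgroup, given an open gate and no subgroup effect.** With independent tests at 5%, the familywise rate is 1 − 0.95^k:

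- k = 4 (one time point): 18.5%. At 4.5% per test it is 16.8%.
- k = 12 (three yearly time points): 46.0%.
- k = 16 (four yearly time points): 56.0%.

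The protocol gives no correlations, so the ranges below rest on assumed values. Results come from multivariate-normal simulation with 200,000 draws per setting, two-sided 5% per test. The first column gives the hip–hip / spine–hip / adjacent-year correlations.

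| Assumed correlations | 4 sites, one time point | 4 sites × 3 years | 4 sites × 4 years | Hochberg + step-down in the subgroup |
|---|---|---|---|---|
| 0 / 0 / 0 | 18.5% | 45.9% | 55.9% | 4.9–5.0% |
| 0.3 / 0.2 / 0.5 | 17.6% | 40.6% | 49.8% | 4.7–4.8% |
| 0.6 / 0.4 / 0.7 | 15.3–15.5% | 32.4% | 39.3% | 4.3% |
| 0.9 / 0.6 / 0.9 | 11.5–11.6% | 19.4% | 22.5% | 3.4% |

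If the step-down over time covers the subgroup, each site must first pass at the last time point, so the one-time-point column applies. The three- and four-year columns apply only if it does not.

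Counting false claims of benefit only, the one-time-point column becomes 9.6%, 8.8–8.9%, 7.6–7.7% and 5.8%, against a nominal 2.5%.

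**4. Error when the drug works in no one.** Running the full gate (Hochberg over five FAS sites plus step-down) at the mid-range correlations gives a subgroup rate of about 0.9%. It cannot exceed the FAS family's 5%, because no subgroup test can succeed without a false FAS result.

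**5. Cost of control.** At the strictest level of a four-site Hochberg, 0.045/4 = 0.01125, power for a 1% difference is still above 99.9%. The difference detectable with 90% power is 0.151 × (1.96 + 1.28) = 0.49% at alpha 0.05, and 0.151 × (2.50 + 1.28) = 0.57% at 0.05/4.

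**The case against.** A reader might infer that the subgroup hypothesis has no multiplicity protection and that its false-positive rate is several times 5% in general. The documents do not support that. Three layers stand before a subgroup claim: a significant morphometric vertebral result, a FAS result at the same site after Hochberg, and, under section 2.7, FAS significance at the same time point, which itself depends on the FAS step-down. With no effect in anyone, these keep the subgroup rate well below 5%.

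A reader might also take the multi-year figures as the main result. The step-down sentences in sections 2.7 and 3.5.5.3 speak of BMD generally and are not limited to the full FAS. Section 3.5.5.1 refers multiplicity to later text just before applying similar analyses to the subgroup. Reading the step-down as covering the subgroup is natural, and the higher figures then fall away. Section 2.5 expects the event target when most patients have 24 to 36 months of treatment, so Month 48 may be exploratory in any case.

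The practical stakes are also limited. At z of about 6.6 under the planning assumptions, adjusted and unadjusted tests agree, and the documents give no reason to expect the BMD effect to vanish in this subgroup. The plan also openly accepts no adjustment across secondary families.

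All of this stands, and it narrows the point without removing it. The waiver is for adjustment across families. Nothing in the text carries Hochberg across the four sites of this one hypothesis.

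**Conclusion.** The point holds in conditional form. When the full-FAS BMD tests are positive and the drug has no BMD effect in bisphosphonate-intolerant patients, the written rules allow about a 12% to 18% two-sided chance of at least one false-positive site at one time point, roughly half of it in the direction of benefit. The range rests on assumed between-site correlations. It rises to about 19% to 56% over three to four yearly time points only on the less natural reading that the BMD step-down over time leaves out the subgroup. Under a global null the gate keeps the rate below 5%. This is a gap in the rule for one formal secondary hypothesis and does not touch the primary endpoints. It is worth closing because the plan already uses the needed method for the same sites and closing it costs almost nothing.

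**What to change.** Add to section 3.5.5.3, and mirror in section 2.7, a statement that within the bisphosphonate-intolerant subgroup:

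- lumbar spine, total hip, femoral neck and trochanter BMD form one family tested by Hochberg;
- the same step-down over time applies as in the full FAS, starting from the last time point performed in at least 50% of patients;
- the FAS gate is retained, and section 3.5.5.3 is aligned with section 2.7 so that it requires FAS significance for the same site at the same time point.

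With this rule the simulated familywise error in the subgroup is 3.4% to 5.0% over all the correlations tried. The cost is the slightly stricter thresholds worked out above: at most 0.08 percentage points on the difference detectable with 90% power, with power for a 1% difference still above 99.9%. No design, data collection or sample size change is needed.

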3.5.5.4 Sample Size and Power Calculations

Underlying Assumptions

Sample size estimates are based on estimates of fracture incidence rates from the Fosamax Fracture Intervention Trial (FIT) data. It is assumed that the expected relative risk (RR) for morphometric vertebral fractures is 0.5, for non-vertebral fractures 0.8 and for hip fractures 0.65². Sample sizes are based on a 4% alpha level at the final analysis (to account for the interim analyses, see multiplicity adjustment section, the final alpha will be $\geq 4\%$) and 90% power.

To ensure enrollment of a study population with adequate overall fracture risk it was decided to have a flexible sample size depending on the observed ratio of number of patients with a prior vertebral fracture to number of patients without prior vertebral fracture. It is expected that the total sample size needed will be smaller if more patients with a prior vertebral fracture can be included.

For the sample size calculations it is assumed that the recruitment period will be approximately 1 year and the total study duration (including the recruitment period) will be approximately 5 years. Other assumptions used to derive the different scenarios are based on estimates from the FIT data and are detailed in Table 3-12.

² In a recent study of the Novartis compound (ASBMR 28th annual meeting -sep 2006 - S16. Abstract #1054 D. Black et. al.) the relative risk for hip fractures was 0.6.

Product: MK-0822

61

Protocol/Amendment No.: 018-04

Table 3-12

Underlying Assumptions Used for Calculations of Sample Size, Based on FIT Data

Patient Population / Fracture Type	Approximate Placebo Fracture Rate	Relative Risk	Drop-out Rate
Patients with no prior vertebral fracture			
Vertebral fractures	4% at 2 years	0.5	10% with no data at all
Hip fractures	1.4% at 3 years	0.65	20% over 3 years
Non-vertebral fractures	8% at 2 years	0.8	13% over 2 years
Patients with 1 prior vertebral fracture			
Vertebral fractures	8% at 2 years	0.5	10% with no data at all
Hip fractures	3% at 3 years	0.65	20% over 3 years
Non-vertebral fractures	11% at 2 years	0.8	13% over 2 years

For the power and sample size calculations the morphometric vertebral fractures endpoint was considered to be binomially distributed at Month 24, the interval-censored survival approach including all patients data available is more powerful. For non-vertebral and hip fractures the primary focus is the number of events needed and time to event methodology was used, with exponential time-to-event and an exponential drop-out mechanism. The s-plus survival procedure using the Lakatos (or Rubinstein) method [26; 27] was used for the sample size and power calculations.

Although enrollment will not be uniform and there will be a Lead Cohort of 1,500 patients randomized earlier in time, sample size calculations are based on uniform enrollment over 1 year as an approximation. It is expected that the 1,500 patients in the Lead Cohort will be enrolled in approximately 3 - 4 months, and that the remaining 15,000 patients in the Main Cohort will be enrolled in approximately 8 months, after a gap of approximately 10 months with no recruitment. This means that the time between the first and last patients enrolled will be about 22 months, with 2 active enrollment periods adding up to a total of approximately 12 months of active recruitment. Due to the uncertainty about the actual enrollment distribution, and due to the fact that additional patient-exposure from the Lead Cohort will translate into a potentially earlier termination of the trial (when all events are seen), it is felt that the uniform distribution over 1 year with a 4 year study duration is a reasonable approximation.

Sample Size Calculations

We will attempt to enroll approximately 4,000 patients with one prior vertebral fracture into the trial. Since the fracture incidence is higher in this group of patients, a lower total number of patients can be included if more patients with a prior vertebral fracture are randomized. If, for example, approximately 3,400 patients with 1 prior vertebral fracture can be recruited in 12 months and 13,600 patients with no prior vertebral fracture (17,000 patients in total), the assumed hip fracture incidence in placebo is approximately

Product: MK-0822

62

Protocol/Amendment No.: 018-04

1.7 based on this ratio of patients with and without prior vertebral fracture, and there will be approximately 90% power ($\alpha=0.04$) to detect a treatment difference of 35% reduction between the treatments for hip fractures, in favor of the odanacatib group. Other scenarios are detailed in Table 3-13.

Table 3-13

Approximate Sample Sizes for Different Ratios of Patients
(Those With and Those Without Prior Vertebral Fractures)
(Assuming 1 Year Recruitment, 4 Year Total Study, $\alpha=0.04$, Power=90%)

Ratio of Patients With to Without Prior Fracture	Hip Fracture Rate in Placebo	Relative Risk	Drop-out Rate Over 3 Years	Number of Events	Approximate Total Number of Patients	Number of Patients Without Prior Fracture	Number of Patients With a Prior Fracture
Alpha = 0.04							
1:5	1.7	0.65	20%	237	17,600	14,650	2,950
1:4	1.7	0.65	20%	237	17,000	13,600	3,400
1:3	1.8	0.65	20%	237	16,300	12,200	4,100
1:2	1.9	0.65	20%	237	15,100	10,050	5,050
1:1	2.2	0.65	20%	236	13,250	6,625	6,625
2:1	2.5	0.65	20%	235	11,800	3,950	7,850

It is expected that approximately 1 out of 4 randomized patients will have a prior vertebral fracture. This means that a total of ~16,300 patients, 12,200 with no prior vertebral fracture and 4,100 with a prior vertebral fracture will have to be randomized. The size of the sample may be revised downward if a higher than anticipated proportion of patients with a prior fracture is enrolled. Conversely, it may be revised upward if a lower than expected proportion of such patients is enrolled. Any such revision will be done in consultation with the Protocol 018 Steering Committee. More detail is below.

Sensitivity Analyses

Table 3-14 provides sample size calculations for a 0.6 relative risk in both groups of patients. It can be seen that sample sizes are highly influenced by the assumed relative risk.

Product: MK-0822

63

Protocol/Amendment No.: 018-04

Table 3-14

Approximate Sample Sizes for Different Ratios of Patients
(Those with and Those without Prior Vertebral Fractures)
(Assuming 1 Year Recruitment, 4 Year Total Study, RR=0.60
in Both Groups, $\alpha=0.04$, power=90%)

Ratio of Patients With to Without Fracture	Hip Fracture Rate in Placebo	Relative Risk	Drop-out Rate Over 3 Years	Number of Events	Approximate Total Number of Patients	Number of Patients Without Prior Fracture	Number of Patients With a Prior Fracture
Alpha = 0.04 - Relative Risk = 0.60 in both groups							
1:4	1.7	0.6	20%	169	12,750	10,200	2,550
1:3	1.8	0.6	20%	169	12,150	9,100	3,050
1:2	1.9	0.6	20%	168	11,300	7,550	3,750
1:1	2.2	0.6	20%	168	9,900	4,950	4,950

Power for Vertebral and Non-vertebral Fractures and BMD

All sample size calculations above are based on the estimates for the hip fracture incidence, since the analyses for morphometric vertebral and non-vertebral fractures have more power than those for hip fractures. For example, if 4,100 patients with one prior vertebral fracture and 12,200 patients without a prior vertebral fracture are randomized into the trial (see Table 3-13), there will be >99% power to detect a treatment difference in morphometric vertebral fractures and in non-vertebral fractures, using the assumptions of Table 3-12 and a significance level of 0.04.

With a total of at least 12,000 patients, there will be >99% power to detect a clinically meaningful BMD difference. For example, assuming that there are 6,000 patients per group, the common standard deviation (SD) is 4%³, alpha is 5% and power of 99% the minimal detectable difference is 0.3%. When 1,200 (10%) patients have a BMD measurement (for distal forearm and total body), a 1% difference can be detected with 99% power ($\alpha=5%$, SD=4%).

Note on Hochberg Procedure

As detailed in Section 3.5.5.3, a combination of a step-down and Hochberg procedure will be used to account for multiplicity due to multiple primary endpoints. This means that if the p-value for non-vertebral fractures is $>\alpha$, hip fractures need to be tested at $\alpha/2$. Similarly, if the p-value for hip fracture is $>\alpha$, then non-vertebral fractures need to be

³ The estimated 4% standard deviation was obtained from the phase IIb study and previous alendronate studies.

Product: MK-0822

64

Protocol/Amendment No.: 018-04

tested at $\alpha/2$. The actual alpha of the final analysis is detailed in Section 3.5.5.6 and will be between 4% and 5%.

To get some idea of the loss in power, the raw powers (not taking multiplicity adjustments or correlations between endpoints into account) for hip and non-vertebral fractures at 2% significance level are also calculated.

Assuming that approximately 16,300 patients (1:3 ratio of patients with to patients without prior vertebral fracture) are randomized and the underlying assumptions are as detailed earlier, then there is >99% power to detect a difference in non-vertebral fractures (RR=0.8) at 2% significance level. Similarly, the raw power for hip fractures is 84% to detect a treatment difference (RR=0.65) with $\alpha=2\%$. Note, as there is >99% to detect a treatment difference in non-vertebral fractures at $\alpha=4\%$, there is minimal chance that the test for hip fractures will need to be performed at $\alpha=2\%$, with the underlying assumptions as before.

Determination of Number of Patients to Enroll

As mentioned earlier, we estimate that a total of 237 hip fractures (first hip fracture per patient) will be needed based on the 1:3 ratio assumption of patients with to patients without a prior vertebral fracture. A total of ~16,300 patients (12,200 with no prior vertebral fracture and 4,100 with a prior vertebral fracture) will therefore have to be randomized. However, the SPONSOR (blinded to treatment assignment) will monitor this ratio regularly during the enrollment period, and calculate the targeted total number of patients to be randomized and the expected total study duration based on the observed ratio of patients with to patients without prior vertebral fracture, and the same assumptions of hip fracture rates as in Table 3-12 and Table 3-13, i.e., 1.4% hip fractures at 3 years for patients without prior vertebral fracture and 3% for those with prior vertebral fracture in the placebo group and an overall relative risk of 0.65, assuming the current recruitment trend continues. If needed, the SPONSOR can decide to stop recruitment in one of the strata, to allow the other stratum to accumulate or they may propose to prolong the enrollment period beyond 1 year, to achieve the necessary total number of patients. The total sample size will be decided upon based on the observed ratio of patients with a prior vertebral fracture to those without a prior vertebral fracture and the expected total study duration, by the SPONSOR.

The roles and responsibilities of the Steering Committee will be detailed in the Steering Committee charter.

Study Termination and Number of Events Needed for Hip, Vertebral and Non-vertebral Fractures

The total number of hip fractures needed to detect a treatment difference (RR=0.65) at 90% power with the underlying assumptions of Table 3-12 is approximately 237 events, the number of non-vertebral fractures is 824, and the number of morphometric vertebral fractures at Month 24 would be 114. Since the analyses are based on time to first fracture,

Product: MK-0822

65

Protocol/Amendment No.: 018-04

the above mentioned number of fractures needed are only the first events per patient. If a patient has, for example, 2 hip fractures, only the first hip fracture will be counted in the above numbers.

During the double-blind therapy period, the Steering Committee and SPONSOR will monitor the number of (first) hip, spine and non-vertebral fracture events observed (blinded) and determine when the study should be terminated. The DMC or the unblinded statistician will not be responsible for determining when the pre-specified number of events are seen, since they are unblinded to study data. Once the SPONSOR, based on the Steering Committee's recommendation, decides to terminate the study, all sites will be informed of this decision and all patients will be requested to come in for their close-out visit as soon as possible after this communication. Once all patients have completed this close-out visit, the database will be locked and unblinded and the final analysis performed.

The Steering Committee and/or Sponsor will also pre-specify a data cut-off date after the last expected close-out visit date. Any fractures or adverse events occurring after the data cut-off will not be included in the final analysis and patients without an event (and who were not discontinued from the trial before) will be censored at this cut-off date, as detailed in Section 3.5.4.

Power for the Analysis in the Subgroup of (Oral) Bisphosphonate Intolerant Patients

It is expected that approximately 1400 patients per group will be (oral) bisphosphonate intolerant and therefore included in the BMD analysis for the corresponding secondary hypothesis. With 1400 patients per group, there is >99% power to detect a 1% difference in percent change from baseline between Odanacatib 50 mg once weekly and placebo, assuming a $\geq 4.5\%$ alpha level (after adjustment for the interim) and a 4% common standard deviation. With a 3% standard deviation this power is also >99%.

